#### **Assessments and Measures**

As illustrated in the **Table**, we will conduct two assessments (separated by one day) at both study entry and completion to objectively measure infant intake and maternal responsiveness. Two brief visits will occur at weeks 2 and 6 to assess infant growth and maternal adherence to the intervention. All assessments will be administered by blinded research assistants.

Study Week:	1	1	2	6	12	12
Assessment Type:	Pre- Test 1*	Pre-Test 2*	Brief visit for	Brief visit for	Post-Test 1*	Post- Test 2*
Bottle used during observation: Clear Bottle Group	Clear	Opaque	growth check	check	Opaque	Clear
Opaque Bottle Group	Opaque	Clear			Clear	Opaque

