### Table. Example Assessment Timeline and Type of Bottles Used during Feeding Observations

\*Home-based assessments within the same week will be separated by one day; conditions will be counterbalanced.

Home-Based Assessments. Two research assistants will visit the mother's home in the morning (to control for infants' circadian rhythms and variations in intake) and will arrive approximately one hour prior to a time when an infant typically takes a bottlefeeding. Mothers will be asked to hide all bottles prior to each visit to ensure research assistants remain blinded. We will call the mother the evening before each visit to assess whether any disruptive events that may negatively influence the infant's behavior (e.g., colds, teething) occurred; if a disruptive event is reported during this phone call, the visit will be rescheduled. After a short acclimation period, we will interview the mother about when the infant last fed and slept and will conduct additional assessments. When the mother and infant are ready to feed, we will set-up two video cameras (GoPro Hero 4, California, USA) at two different angles (to obtain clear views of both the mother and the infant) ~10 feet in front of a location where the mother typically bottle-feeds her infant and will record the mother feeding her infant using clear or opaque bottles. The mother will be instructed to feed her infant as she normally would at home and the research assistants will wait in another room to minimize any possible influence on the mother's or infant's feeding behaviors. Additional questionnaires will be completed after feeding.

**Measures.** We will evaluate our intervention along multiple dimensions to fully understand the impact of opaque bottles on feeding outcomes and the feasibility of scaling this intervention for larger trials.

- **Infant intake** will be assessed by weighing the infant's bottle before and after each feeding observation using a top-loading balance (SP601 Scout Pro Portable Balance, Ohaus, New Jersey, USA). We will also note the type of nipple used and will control for nipple flow rate in all analyses.

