- Feasibility, Fidelity, Adherence, and Acceptability will be assessed through a number of objective and subjective measures (see Appendix 5). Feasibility of recruitment and retention will be evaluated by: (a) tracking the number of women who respond to advertisements, are eligible, but decline participation; (b) examining whether recruitment targets are met across different ethnic/racial strata; (c) assessing the number of participants who agree to participate but drop out or are lost to followup, and determining reasons for drop out. To assess feasibility and fidelity of treatment conditions, interventionists will track distribution of the informational brochure (in each group) and brief phone calls completed. We will ask participants about any crossbottle usage (e.g., the *clear* group using opaque bottles or *vice versa*). Adherence will be assessed by mothers' self-reports of the extent to which they used their assigned bottles (i.e., estimated percentage of feedings) at the 2-, 6-, and 12-week assessments. During these assessments, we will also assess whether infants experienced any illnesses that might have interfered with their typical feeding behaviors or weight gain, or whether mothers changed bottles, nipples, or formulas. We will also objectively measure bottle-usage and feeding patterns by affixing a light-weight, proprietary intake-tracking device to the bottoms of the bottles of all mothers within both the control and intervention groups. We developed this device to allow for objective and unobtrusive tracking of infants' intake in free-living settings; the device tracks infant feeding patterns by assessing the weight of the bottle before and after each feeding and time stamping each feed start and end. The device is dishwasher safe and has the capacity to store 6-months of feeding data, thus can be used for the entire duration of the proposed study. Although this device is still under development, preliminary tests have shown it is highly valid, with measurement error <0.05 oz. Acceptability will be

assessed by querying mothers about their perceptions of their bottles and any barriers to use of the bottles.

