#### **Statistical Considerations**

Data Analysis. All quantitative analyses will be conducted using SAS v.9.4 (SAS Institute Inc., North Carolina, USA). Oualitative interview data will be transcribed and sorted into thematic categories using constant comparison within the framework of grounded theory. We will use linear regression to model the change in infant intake and maternal responsiveness (Aim 1) and change in WLZ, skinfolds, waist circumference (Aim 2) by the primary study variable of *clear* versus *opaque* group. For Aim 3, we will examine the feasibility, fidelity, adherence, acceptability, and safety of the intervention by summarizing quantitative and qualitative data related to recruitment and retention, mothers' use of their assigned bottles, perceptions of and barriers to using the bottles, and any issues related to infant inadequate weight gain or weight loss. We will then explore whether variations in intervention feasibility, fidelity, adherence, acceptability or safety are correlated with baseline characteristics of mothers (e.g., weight status, race/ethnicity, socioeconomic status, parity, feeding practices and styles, non-maternal caregiver involvement in feeding) and infants (e.g., sex, birth weight, weight status, temperament). Finally, we will assess whether the effects of the intervention on infant intake, maternal responsiveness, and infant WLZ change are moderated by the following factors: nipple type; mothers' adherence to the intervention, race/ethnicity, parity, or feeding practices and styles; infants' sex, temperament, and timing of solid food introduction; and the extent to which non-maternal caregivers are feeding the infant. Moderation will be explored by including a group by moderator interaction term in the linear regression models used to explore Aims 1 and 2. All inferential analyses will be preceded by appropriate descriptive statistics and graphs to determine that assumptions for linear regression are satisfied.

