Infants who exhibit slower than expected growth will be referred to their pediatrician or emergency services for further consultation and will be removed from the study if the PI and/or DSM deem study participation harmful to the infant or family.

We will also employ strategies we have used in previous studies to minimize discomfort, including having familiar research staff present in the homes during assessments, and moving to another room or outside the home (if another room is not available) during video-recorded feeding interactions. The PI has significant expertise in coding video-recorded feeding interactions and ensuring mother and infant comfort and confidentiality during this process. Furthermore, all research assistants will be trained to ensure that assessments are conducted in a professional and nonjudgmental manner.

Adverse events determined by the PI to be unanticipated problems involving risks to subjects or to others will be reported by the PI to the IRB within 10 days. Adverse events that are reviewed by the PI and not determined to be unanticipated problems involving

risks to subjects or to others will be reported per IRB policy at the time of continuing review.

All study personnel will be informed by the PI about any unanticipated problems involving risks to subjects or to others. If any protocol changes are needed, the PI will submit a modification request to the IRB. Protocol changes will not be implemented prior to the IRB approval unless necessary to eliminate apparent immediate hazards to the research participants. In such a case, the IRB will be promptly notified of the change following implementation (within 10 working days). Protocol adherence will be monitored by the PI during bi-monthly meetings with the research assistants. If the PI is made aware of an unanticipated protocol deviation, the PI will report this deviation to the IRB within 10 days.

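### Mothers report bottle use at visits run by blinded assistants, and no stated step covers what they say, so a disclosure could carry into the week 12 growth measures

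*Combined protocol and SAP*

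**What the plan says.** All references are to the combined protocol and SAP.

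- **Who runs the visits.** Assessments and Measures: "All assessments will be administered by blinded research assistants".
- **What the brief visits contain.** Same section: "Two brief visits will occur at weeks 2 and 6 to assess infant growth and maternal adherence to the intervention".
- **What mothers report.** Under Measures (Feasibility, Fidelity, Adherence, and Acceptability), adherence is the mother's own report of how far she "used their assigned bottles (i.e., estimated percentage of feedings) at the 2-, 6-, and 12-week assessments". The same assessments cover "whether mothers changed bottles, nipples, or formulas". Cross-use of the other group's bottles, perceptions and barriers are also queried, with no interviewer named. The instruments are placed in Appendix 5, which is not in the text reviewed.
- **Interviews.** Under Data Analysis, qualitative "interview data will be transcribed and sorted into thematic categories using constant comparison", and the Aim 3 summaries draw on quantitative and qualitative data about mothers' "use of their assigned bottles, perceptions of and barriers to using the bottles". Who interviews, and when, is not stated.
- **Protection of blinding.** Under Home-Based Assessments, mothers hide their bottles before each visit, and the stated purpose is to keep assistants blind. Under Randomization, separate unblinded assistants tell mothers their group at the end of Pre-Test 2. Under Experimental Conditions, an interventionist phones monthly.
- **Continuity of staff.** The data safety and monitoring section lists, as a comfort measure, "having familiar research staff present in the homes during assessments".

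**The concern.** The plan treats the blinding of visit staff as worth protecting, but the step it takes guards only against sight. Mothers are then asked about their bottles within visits assigned to those staff. A mother who says what she has been using tells the assistant her group.

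At stake is the Aim 2 growth contrast. Length, skinfold thickness and waist circumference depend on how the operator positions the infant, applies the instrument and reads it. Length feeds directly into WLZ. An assistant who knows the group and expects slower growth with opaque bottles could shift these readings without intending to. Triplicate readings, stated for weight and height, reduce random error but do not remove a consistent lean.

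**Working it through.** No figure in the plan is in dispute, so the check sets the passages side by side and follows the route from a mother's report to an outcome.

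**1. Do bottle-use reports fall within blinded visits?** Yes. Assessments and Measures gives every assessment to blinded assistants and names adherence as part of the week 2 and 6 visits. The Measures section places the adherence report and the bottle-change question at weeks 2, 6 and 12. Neither place assigns these items to the unblinded assistants or the interventionist.

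**2. Does a stated safeguard cover speech?** Three features help, but none reaches this.
- Hiding bottles prevents sight of them.
- Using separate staff to reveal the group, and for the monthly calls, keeps those conversations away from assessors.
- Observing both bottle types in both groups stops the observed bottle from revealing the group.

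The text reviewed contains no instruction to mothers not to name their group, no sealed form, and no separation of the person who asks from the person who measures.

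**3. Must the report reveal the group?** No. A percentage of feeds from assigned bottles can be given in either group without naming the bottle. Questions on cross-use, perceptions and barriers are harder to answer neutrally. The planned interview transcripts make some spoken reporting likely, but do not place it with the assessors. At home-based assessments staff also "we will interview the mother about when the infant last fed and slept and will conduct additional assessments"; that is spoken contact before the feed, but its stated topics are feeding and sleep times, not bottle type.

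**4. Which measurements could be reached?**

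| Measurement | Could a disclosure precede it? | Reason |
|---|---|---|
| Baseline growth | No | Mothers learn their group only at the end of Pre-Test 2 |
| Week 2 and 6 growth | Possibly | No order is stated within the brief visits, but Aim 2 compares study start with study end, so these values do not enter that contrast |
| Post-Test 1 growth | Only by carry-over from week 2 or 6 | Infants are measured before the feed; additional questionnaires follow it |
| Post-Test 2 growth | By carry-over from week 2, 6 or Post-Test 1 | As above, with Post-Test 1 questionnaires already completed |
| Intake (Aim 1) | Little scope | Bottle weighed on a balance; staff leave the room during the feed |
| Responsiveness (Aim 1) | Not by this route | Coded from video by separate coders who do not know the conditions |

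**5. What does carry-over need?** The mother discloses; the same assistant returns at week 12, which is 12 − 6 = 6 weeks or 12 − 2 = 10 weeks later; that assistant remembers and takes an operator-dependent measurement; and the reading shifts differently by group. The plan for familiar staff makes the return plausible but does not state it.

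**The case against.** The strongest reply is that the question turns on an instrument outside the text reviewed. If the items in Appendix 5 are self-completed and returned unseen, the route is largely closed and one clarifying sentence would do. The adherence item can be answered neutrally, and blinded staff can collect a neutral percentage without contradiction. Familiar staff are mentioned only for participants' comfort, and two assistants attend each home-based assessment, so the person who hears need not be the person who measures. Post-Test 1 already yields week 12 anthropometry before that visit's questionnaires.

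All of this stands, and it limits the point to a possible route. It does not remove the gap: the plan assigns bottle-use reporting to visits run by staff who must stay blind, and no stated step covers what is said there.

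A reader might infer more in two ways. One is that assessor blinding fails, or that the plan contradicts itself; the documents show neither. The other is that a loss of power or a rise in false positives can be attached to this. It cannot: the documents give no size for assessor bias and no frequency of disclosure, so any such figure would only restate an assumed shift.

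**Conclusion.** The concern holds in a narrow form. Spoken disclosure at visits run by blinded assistants is possible and unguarded in the text. Its plausible reach is week 12 length (hence WLZ), skinfolds and waist, through carry-over from week 2 or 6 if the same staff return. Disclosure at Post-Test 1 could affect only Post-Test 2 measures.

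The size of any bias is unknown, and none is claimed. The conclusion rests on two assumptions that the documents leave open: that at least some bottle items are spoken to, or seen by, assessors, and that an assistant who learns the group later measures the same infant. Severity is minor and confidence is medium. The case for acting is that the remedy costs little.

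**What to change.** - Collect the adherence, bottle-change, cross-use and acceptability items on a sealed or online self-completed form, in English and Spanish, that assessors do not see. Alternatively, use the existing unblinded assistants or the interventionist. If Appendix 5 is already self-completed, it is enough to state that assessors do not see the answers.
- Have any interview on bottle use, perceptions or barriers held by unblinded staff.
- Place any bottle item left within a visit after all anthropometry; at week 12, after the Post-Test 2 anthropometry. Ordering alone does not stop carry-over from week 2 or 6, so it supplements the first step and does not replace it.
- Instruct mothers not to tell assessors their group.

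**Cost.** Protocol wording and one short form in two languages at weeks 2, 6 and 12, with little extra staff time. The downside is a slight change in the mode or timing of adherence recall. If the phone route is chosen, the monthly calls do not line up with weeks 2, 6 and 12, so extra calls would be needed.

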### Table. Example Assessment Timeline and Type of Bottles Used during Feeding Observations

\*Home-based assessments within the same week will be separated by one day; conditions will be counterbalanced.

Home-Based Assessments. Two research assistants will visit the mother's home in the morning (to control for infants' circadian rhythms and variations in intake) and will arrive approximately one hour prior to a time when an infant typically takes a bottlefeeding. Mothers will be asked to hide all bottles prior to each visit to ensure research assistants remain blinded. We will call the mother the evening before each visit to assess whether any disruptive events that may negatively influence the infant's behavior (e.g., colds, teething) occurred; if a disruptive event is reported during this phone call, the visit will be rescheduled. After a short acclimation period, we will interview the mother about when the infant last fed and slept and will conduct additional assessments. When the mother and infant are ready to feed, we will set-up two video cameras (GoPro Hero 4, California, USA) at two different angles (to obtain clear views of both the mother and the infant) ~10 feet in front of a location where the mother typically bottle-feeds her infant and will record the mother feeding her infant using clear or opaque bottles. The mother will be instructed to feed her infant as she normally would at home and the research assistants will wait in another room to minimize any possible influence on the mother's or infant's feeding behaviors. Additional questionnaires will be completed after feeding.

**Measures.** We will evaluate our intervention along multiple dimensions to fully understand the impact of opaque bottles on feeding outcomes and the feasibility of scaling this intervention for larger trials.

- **Infant intake** will be assessed by weighing the infant's bottle before and after each feeding observation using a top-loading balance (SP601 Scout Pro Portable Balance, Ohaus, New Jersey, USA). We will also note the type of nipple used and will control for nipple flow rate in all analyses.
- Maternal responsiveness to infant cues will be objectively assessed by video-coding of all feeding observations. After each visit, three trained coders who are unaware of the experimental conditions and hypotheses of the study will code videos using the NCAFS, a reliable and valid means of observing and rating mother-child interactions during a feeding session. The NCAFS is validated for use with mothers and their 0-1-year-old infants, can be applied to a breast or bottle-feeding episodes, and has been used during both lab- and home-based feeding observations. It contains 76 observable behaviors that are organized into six subscales; for the proposed research, we will

focus the Maternal Sensitivity to Infant Cues subscale. Reliability will be established prior to full coding of all videos. To this end, coders will code 10 common videos, and will double-code 10 additional videos. Inter-coder comparison of the 10 common videos will be used to establish inter-coder reliability. Intra-coder comparison of the 10 double-coded videos will be used to establish intra-coder reliability. Full coding will not commence until a Kappa > 0.80 is reached for all coders. The PI is certified in this coding system and has it previously.

- Maternal feeding style, including responsive and pressuring feeding, will also be subjectively assessed at study entry and completion using the Infant Feeding Style Questionnaire (IFSQ; see Appendix 4), which assesses maternal behaviors (e.g., control) and beliefs (e.g., concern about feeding) related to infant feeding. This scale has been validated in diverse samples of mothers with young infants and the PI has used this measure in previous research.
- Infant growth will be assessed during all home-based assessments by trained research assistants measuring infant weight and height in triplicate using a portable infant scale/infantometer (models 334 and 233; Seca, Hamburg, Germany). To minimize bias, infants will always be weighed and measured while only wearing a clean diaper and prior to the observed feeding. We will use the World Health Organization (WHO) Anthro software version 3.0.1 (http://www.who.int/childgrowth/en/) to calculate age-and sex-specific weight-for-length z-scores (WLZ) based on the WHO growth standards. We will also assess infant adiposity by infant skin-fold thickness and waist circumference using standard protocols.
- Feasibility, Fidelity, Adherence, and Acceptability will be assessed through a number of objective and subjective measures (see Appendix 5). Feasibility of recruitment and retention will be evaluated by: (a) tracking the number of women who respond to advertisements, are eligible, but decline participation; (b) examining whether recruitment targets are met across different ethnic/racial strata; (c) assessing the number of participants who agree to participate but drop out or are lost to followup, and determining reasons for drop out. To assess feasibility and fidelity of treatment conditions, interventionists will track distribution of the informational brochure (in each group) and brief phone calls completed. We will ask participants about any crossbottle usage (e.g., the *clear* group using opaque bottles or *vice versa*). Adherence will be assessed by mothers' self-reports of the extent to which they used their assigned bottles (i.e., estimated percentage of feedings) at the 2-, 6-, and 12-week assessments. During these assessments, we will also assess whether infants experienced any illnesses that might have interfered with their typical feeding behaviors or weight gain, or whether mothers changed bottles, nipples, or formulas. We will also objectively measure bottle-usage and feeding patterns by affixing a light-weight, proprietary intake-tracking device to the bottoms of the bottles of all mothers within both the control and intervention groups. We developed this device to allow for objective and unobtrusive tracking of infants' intake in free-living settings; the device tracks infant feeding patterns by assessing the weight of the bottle before and after each feeding and time stamping each feed start and end. The device is dishwasher safe and has the capacity to store 6-months of feeding data, thus can be used for the entire duration of the proposed study. Although this device is still under development, preliminary tests have shown it is highly valid, with measurement error <0.05 oz. Acceptability will be

assessed by querying mothers about their perceptions of their bottles and any barriers to use of the bottles.

Additional potential moderators of intervention effects: We will also assess: infant sex; infant temperament, assessed by the Infant Behavior Questionnaire-Revised Very Short Form (IBQ-RVS; see Appendix 6); infant feeding history, including if and when solid foods are introduced, assessed by maternal retrospective report (see Appendix 7); maternal weight status, assessed using an adult scale/stadiometer (models 876 and 213; Seca, Hamburg, Germany) during the home-based assessments and through self-reported pre-pregnancy weight and gestational weight gain (see **Appendix 8**); family demographics, including parity, marital status, maternal education, race/ethnicity, assessed by a demographic questionnaire (see Appendix 9); maternal perceptions of the infant's eating behaviors (e.g., satiety responsiveness, food responsiveness) via the Baby Eating Behaviors Questionnaire (BEBQ; see Appendix 10); mothers' parenting confidence (see Appendix 11); mothers' level of distracted parenting (see Appendix 12); and non-maternal caregivers' involvement in child feeding assessed using the Non-Maternal Caregivers questionnaire from the Infant Care, Feeding and Risk of Obesity Study, a measure that queries mothers about the frequency to which anyone, other than themselves, was responsible for feeding their infants on a typical day (see Appendix 13).

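### Aim 1 has no day or order term although bottle order is counterbalanced: a small, conditional loss of precision if change is taken on a single bottle

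*Combined protocol and SAP*

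**What the plan says.** The Combined protocol and SAP, under Assessments and Measures, plans paired visits: "we will conduct two assessments (separated by one day) at both study entry and completion". The Table's rows "Bottle used during observation: Clear Bottle Group" and "Opaque Bottle Group" give the bottle filmed at each visit:

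- Clear group: clear then opaque at entry; opaque then clear at week 12.
- Opaque group: opaque then clear at entry; clear then opaque at week 12.

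The Table is headed "Table. Example Assessment Timeline and Type of Bottles Used during Feeding Observations", and its footnote reads "Home-based assessments within the same week will be separated by one day; conditions will be counterbalanced". The counterbalancing scheme is not described further.

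Under Statistical Considerations, Data Analysis, the Aim 1 model is "We will use linear regression to model the change in infant intake and maternal responsiveness (Aim 1"), "by the primary study variable of *clear* versus *opaque* group". The only adjustment named for every analysis is in the infant intake measure: "We will also note the type of nipple used and will control for nipple flow rate in all analyses". Visit day, bottle order and observation bottle are neither model terms nor listed moderators. The plan does not say whether change is computed on the assigned bottle, on one fixed bottle, or on the mean of both feeds.

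**The concern.** Bottle order is a factor that the design balances deliberately. If second-day feeds differ from first-day feeds, for instance because staff and cameras are less novel, a single-bottle change computed under the reversed order picks up the day effect with one sign for half the dyads and the opposite sign for the other half. Balance within arm keeps this out of the group contrast. With no term in the model, however, it stays in the residual, widens the confidence interval and makes the test conservative. The design has already paid for removing this variance, and the analysis does not collect the benefit.

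**Working it through.** **Inputs.** From Power calculations: n = 100, intake SD 33.7 mL, NCAFS SD 1.91, correlation of baseline with week 12 of .55 (clear) and .40 (opaque), α = .05, 80% power. Assumed: 50 per arm, a two-sided test, order split 50:50 within arm. The day effect (day 2 minus day 1) is not in the documents; 5, 10 and 15 mL are used.

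**The plan's own figure.** Change variance per arm is 2·SD²·(1−r). The average over arms is 33.7² × (0.90 + 1.20)/2 = 1135.69 × 1.05 = 1192.5 mL² (SD 34.5). The standard error is √(2 × 1192.5/50) = 6.91, and the detectable difference is (1.960 + 0.842) × 6.91 = 19.35 mL. The plan states 19.1 mL, which has power 0.790 on these inputs, so its figure is reproduced closely. The comparisons below use 19.35 mL, where power is 0.80.

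**How the day effect enters.** Let d1 be the day effect at entry and d2 at week 12. With reversed order:
- bottle filmed on day 1 at entry and day 2 at week 12: the change carries +d2;
- bottle filmed on day 2 at entry and day 1 at week 12: the change carries −d1.

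The two orders differ by d1 + d2. A 50:50 split therefore adds ((d1+d2)/2)² to the residual variance: d² if the effects are equal, d²/4 if the effect has gone by week 12.

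| Assumed d | Case | Added variance | Increase | Detectable difference | Power for 19.35 mL |
|---|---|---|---|---|---|
| 5 mL | equal | 25 | 2.1% | 19.55 mL | 0.792 |
| 5 mL | entry only | 6.25 | 0.5% | 19.40 mL | 0.798 |
| 10 mL | equal | 100 | 8.4% | 20.14 mL | 0.768 |
| 10 mL | entry only | 25 | 2.1% | 19.55 mL | 0.792 |
| 15 mL | equal | 225 | 18.9% | 21.10 mL | 0.729 |
| 15 mL | entry only | 56.25 | 4.7% | 19.80 mL | 0.782 |

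If order were drawn independently at each time point, equal effects would add d²/2 (at 10 mL: 50 mL², 4.2%, power 0.784). If both feeds at a time point are averaged, every dyad's change carries (d2−d1)/2 and nothing is added.

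**Bias or noise.** In 6,000 simulated trials (fixed-bottle change, equal effects of 10 mL, exact balance within arm) the mean estimate was −19.34 mL without the order term and −19.27 with it, for a true −19.35. Power was 0.766 and 0.791. With no true difference, the rejection rate was 0.038 without the term and 0.049 with it. Under exact balance the estimate itself is no more variable; the loss comes from a reported standard error that is too large, √(2 × 1292.5/50) = 7.19 instead of 6.91.

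**Coding of the term.** For a fixed-bottle change, a clear-first indicator absorbs the effect. For an assigned-bottle change it does not: a clear-first dyad carries one sign in the clear arm and the other in the opaque arm, so the indicator's main effect is zero. At 10 mL, simulated power for the assigned-bottle change was 0.765 with and without a clear-first term. Coding order as assigned bottle first, or adding order by group, restores it to about 0.80.

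**NCAFS.** Change variance is 1.91² × 1.05 = 3.83. An assumed 0.5-point day effect, equal at both times, adds 0.25/3.83 = 6.5%. These inputs give a detectable difference of 1.10, which becomes 1.10 × √1.065 = 1.14, still below the stated 1.32.

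**The case against.** The strongest reply is that the loss is hypothetical. The documents give no day effect. The reversal is shown only in a Table labelled as an example. The outcome may be the average of both feeds, in which case nothing is lost. If novelty is the cause, it should have faded by week 12 after repeated visits, which quarters the added variance. In a pilot-feasibility study, a gain of one or two points of power is modest. All of this stands, and it is why the point is minor. It does not remove the point: under any single-bottle reading with a non-zero net day effect, the term recovers precision for almost nothing.

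Two stronger readings are tempting.

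- A reader might infer that the planned power is missed. That cannot be shown. The SDs come from a pilot study, and the documents do not say whether they already contain day or order variation. If they do, the stated power is not overstated and the term would only improve on it.
- A reader might take the Table's rows as the fixed order for each arm. A fixed-bottle change would then carry opposite day effects in the two arms, a bias of 2d (20 mL at d = 10) that no order term could separate from group, while an assigned-bottle change would carry the same shift in both arms and cancel. The footnote's counterbalancing and the example label point instead to balance within arm. The plan should still say so.

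**Conclusion.** The point holds as a minor loss of precision, not as bias. It rests on order being balanced within arm, change being taken on a single bottle, and a day effect that does not net to zero across entry and week 12. The plausible cost at an assumed 10 mL is 1 to 3 points of power for intake, depending on whether the effect persists to week 12. At 15 mL it is about 2 points (entry only) to 7 points (equal effects). A further, smaller benefit of the term is protection if dropout unbalances order. As an illustration, completers split 55:45 in one arm and 45:55 in the other would shift an unadjusted fixed-bottle contrast by 0.2d, or 2 mL at d = 10 with equal effects.

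**What to change.** In Data Analysis, state which feed or feeds form the Aim 1 change, and add an order term matched to that choice:

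- fixed-bottle change: an indicator for clear bottle first at entry;
- assigned-bottle change: an indicator for assigned bottle first at entry, or equivalently order, group and order by group;
- mean of both feeds: no term is needed, and one does no harm.

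Alternatively, fit one mixed model to all four feeds with group, time, observation bottle and visit day within each time point, and name the group-by-time contrast that answers Aim 1.

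In the Table footnote, state that order is balanced within each arm and recorded for each dyad. Keeping each dyad's order the same at week 12 is an optional alternative, but it leaves ((d2−d1)/2)² in the variance and so cancels only a day effect that is equal at both times.

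The cost is a few sentences and one or two degrees of freedom (100 − 3 = 97 remain after intercept, group and one order term, before nipple flow rate). No new visits or measurements are needed.
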